#### 3.3 COVERAGE ASSESSMENT

Potential coverage increases in the intervention arms compared to the control arm (second objective) will be analysed by conducting baseline and endline assessments using the 'Simplified lot quality assurance sampling evaluation of access and coverage' (SLEAC) methodology. This had been specifically designed for community-based management of SAM and it combines routine programme monitoring data and small-sample quantitative survey. It also provides some information related to barriers of access.

The intervention seeks to improve following Sphere indicators as:

- Percentage of target population that can access on-site programmers within one hour (it should be >90%). As 60% of people in Mali are living more than 5km from the HF, achieving this will be only possible if we work directly with CHWs
- Percentage of SAM cases with access to treatment services (it should be >50% rural areas). The actual coverage is under 30%.

#### 3.4 COST-EFFECTIVENESS ANALYSIS

For the cost-effectiveness analysis (fourth objective), it will be carried out from a societal perspective. An activity-based costing method will be applied by collecting data from accounting records and information from structured interviews with key stakeholders. Costs linked to research only will be excluded. Cost will reflect only treatment of non-complicated SAM cases. We will present costs for different cost centres per arm, calculate cost-efficiency and incremental cost-effectiveness ratio for children cured (comparing children in the intervention arms 2 and 3 vs. control arm with standard

CMAM protocol rather than a do nothing attitude) and DALYs. A sensitivity analysis will be conducted. The team has previous experience performing this type of analysis in non-emergency settings in Mali.

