#### 2.2.2 SPECIFIC OBJECTIVES

- ✓ To determine if CHWs can treat SAM children and respect the SPHERE standards in an emergency setting;
- ✓ To assess whether coverage increases by including SAM treatment within iCCM package delivered by CHWs in an emergency setting;
- ✓ To assess whether CHWs can effectively use a combined/simplified protocol to treat SAM children in an emergency setting;
- ✓ To analyze cost and cost-effectiveness of three different models of SAM treatment.
- ✓ To analyze the impact of integrating SAM management in iCCM on CHW workload (just for Senegal)

[figure not shown]

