#### 3.2.2 CHILDREN'S ENROLLMENT

The sample will consist of children aged 6-59 months with uncomplicated SAM. In all arms children with severe edema, failing appetite test or having other severe medical complications will be excluded (they will be referred for inpatient treatment). In the arms with CMAM protocol inclusion, criteria will be: bilateral pitting edema (+/++) and/or weight-for-height below -3 Zscore of the World Health Organization Growth Reference and/or MUAC<115mm. In the intervention arm 2, the combined/simplified protocol considers just bilateral pitting edema (+/++) and/or MUAC as only anthropometric admission criteria.

SAM children enrolled in treatment with the CMAM protocol will receive RUTF doses according to their weight (200Kcal/kg/day) whilst those in the combined/simplified protocol will receive a fixed quantity (two sachets RUTF=1000Kcal/day). MAM treatment will be assured in all arms consisting of 500Kcal/day (CMAM: 1 sachet RUSF; Combined/Simplified: 1 sachet RUTF) although MAM children will not be included in analysis. The prevalence of MAM usually triples that of SAM and including MAM data would imply a huge increase in sample size and the need of hiring more supervisors to collect disaggregated data and to keep data quality. This economical overrun couldn't be assumed by the project's budget.

In all arms, discharge criteria will be: absence of edema and reaching the anthropometric cut-off point and maintaining these criteria for two consecutive visits. In CMAM protocol, this depends on the reason for admission (weight-for-height  $\geq$  - 1.5 Zscore or MUAC  $\geq$ 125 mm) and in the combined/simplified protocol it is only MUAC  $\geq$ 125 mm.

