#### 3.2.3 DATA COLLECTION AND ANALYSIS

The comparability of the three arms is assumed due to randomization process but even so, it is intended that carers of the children enrolled will complete a short socio-economic survey at admission containing questions related to characteristics of household, livelihoods, hygiene practices and health services utilization according to the Demographic and Health Surveys Program methodology, as well as a Household Dietary Diversity Score. Those socio-economic variables will enable us to describe the sample and they will be used as possible confounders for the adjustment of regressions and risks analysis and to explore which of that has more impact on children's recovery in each arm.

To achieve our objectives, we will consider two main independent variables:

- Treatment provider (HC vs. HC+CHWs)
- Protocol applied in the case of CHWs areas (CMAM vs. Combined/Simplified).

The dependent variables to compare within SAM children (enrolled with MUAC<115mm in the three arms) will be the rates of: recovery (discharge as cured), default (children absent from treatment two consecutive follow-up visits), unresponsiveness (children not improving their nutritional status in two consecutive visits), transfer to inpatient treatment due to health complications and death.

Other variables to be compared will be severity at admission (MUAC measurement and presence of edema), prevalence of non-severe complications at admission and during treatment, treatment length and average daily weight and MUAC gain. Other routine information will be recorded monthly such as referral records and stock supplies.

Disaggregated data on the study subjects will firstly be recorded on paper (patient cards) by HC staff and CHWs according to the specific requirements of the MoH. The data will then be periodically reported by the supervisors via tablet using KOBO software which allows control of transcription errors improving data quality.

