#### 4.3 ETHICAL CONSIDERATIONS

The study protocol will be submitted for review to the Spanish Ethical Committee assigned to the Complutense University of Madrid ("Comité de Ética Clínica Hospital Clínico San Carlos"), the Ethical Committees of academic institutions of both countries (Mali and Sengeal) and

The following principles will be adopted:

- Upon approval of the protocol, ACF in Mali/Senegal will inform the local and regional health authorities and the community representatives. The objective and procedures of the study will be explained to the caregiver. All the applicants will have the right to refuse participation in the study. Each CHW will be asked to read the voluntary and informed consent declaration in its entirety, slowly and in the local language of the participant. The CHW will then ask if the consent declaration was understood, and if there are any questions.
- √ The CHW will ask the caregiver if she or he agrees to participate in the study. At that
  moment, the opportunity to refuse participation in the study will be given to the
  applicant. The CHW will explain that it is possible to withdraw participation at any
  point in the study, without any repercussions on the patient or her/his family.
  Voluntary and informed consent for children will be given by the parents or legal
  guardian. A voluntary and informed consent form will be signed (or fingerprinted) by
  the principal caretaker, and, if present, the head of household. Those who refuse to
  participate will benefit from the same treatment as the other children, but their data
  will not be included in the study.
- Emergencies: Every participant in the study, whether in a control and intervention arms, will benefit from medical care in the event of medical complications linked to a change in their nutritional status during the study. The program will bear medical expenses related to these interventions. Acute malnutrition treatment is nevertheless available for free in every healthcare centre.
- Declaration of conflicting interests: Research team's sole interest is to contribute to an improvement in SAM treatment coverage and thus to an improvement in access to healthcare for remote communities with no treatment facilities, as well as to improve equity in iCCM care.

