#### 5 RESEARCH IMPACT

#### 5.1 EXPECTED RESULTS

This intervention it is expected to contribute to an improvement in access to care during humanitarian crises and a reduction in the number of children dropping out of acute malnutrition management programs. The advantages of this approach are the early diagnosis and care of malnourished children, which could lead to a reduction in the development of medical complications and impact on the health costs for households.

More cost-effective interventions will also allow health authorities to develop strategies for reaching a higher number of malnourished children during crises.

By improving CHW's capacities, and integrating SAM management into the iCCM package, the intervention also aims to have a positive impact on the management of other illnesses with a high mortality rate (diarrhoea, malaria and pneumonia).

The results generated by this research could provide key evidence for the full scale-up of this approach at country-level and in the Sahel region, improving SAM treatment coverage and contributing to a reduction in child mortality, particularly during humanitarian crises.

The specific results expected from the research are:

- 1) Effectiveness of a new intervention model with CHWs
- Evidence on the performance of the SAM care delivered by CHWs: Non-inferiority of the cure rate of children receiving care from the CHWs (greater or equal to the care provided by staff at HC).
- Evidence on the performance of the SAM care delivered using the simplified/combined protocol: Non-inferiority of the cure rate of children receiving care with this protocol.
- Evidence of an increase in the coverage of SAM treatment, in the health areas where treatment is available at HC level and CHW sites.
- 2) Contribution to the continuity of care
- Improvement of the continuum of care for SAM children across all levels of the health pyramid, starting from the Hospital Referral Health Centre (for SAM children with complications), to the HC (for SAM children without complications
   CMAM Approach), through to community-level care delivered by CHWs (for SAM children without complications - iCCM approach).
- 3) Cost-effectiveness of the intervention
- Cost-effectiveness analysis of the different models of SAM treatment: with the hypothesis of sharing the costs already in place for the iCCM intervention, but with an increase in the provision of services including SAM in the Community Primary Healthcare services package.

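### The planned ICERs compare the CHW models with control and announce no increment between them, and the cost-scope sentence, read literally, omits inpatient care of enrolled children who are later transferred

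*Protocol*

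**What the plan says.** The fourth specific objective (section 2.2.2) is: "To analyze cost and cost-effectiveness of three different models of SAM treatment".

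Section 3.4 carries it out. On perspective: "it will be carried out from a societal perspective". On scope: "Cost will reflect only treatment of non-complicated SAM cases". The ICER per child cured is defined by "comparing children in the intervention arms 2 and 3 vs. control arm with standard" CMAM, and DALYs are also named. Costs are to be presented per arm by cost centre, and a sensitivity analysis is announced without content.

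Four other places bear on this:

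- Section 3.2.3 names two main independent variables. One is the protocol used in CHW areas, CMAM or combined/simplified. Its compared outcomes include "transfer to inpatient treatment due to health complications and death".
- Section 3.2.2 does not enrol children with severe complications at admission. They are referred to inpatient care.
- Section 4.3 covers complications during the study: "The program will bear medical expenses related to these interventions".
- Section 5.1 expects early diagnosis and care, "which could lead to a reduction in the development of medical complications and impact on the health costs for households".

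**The concern.** The three models are mutually exclusive choices for a health authority. With a common comparator, each ratio shows whether a model is worth having instead of control. It does not show which of the two CHW models to choose. A model that is dominated by the other can still have a favourable ratio against control, and a model that buys very little over the other can look reasonable because most of its gain was already available more cheaply. The trial treats the CHW-CMAM versus CHW-combined contrast as central for effectiveness, but the economic section does not announce it.

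The scope sentence raises a second, softer problem. Taken as written, it removes the inpatient cost of a child who was enrolled without complications and deteriorated. That cost is really incurred, and the programme pays it. The health consequences can still enter through cures and DALYs, so costs and effects would not follow the same pathway. A model that prevents transfers would get no cost credit, and one with more transfers would not be charged for them.

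**Working it through.** The protocol states no unit cost, ICER or threshold, so there is no figure of its own to reproduce. The check is whether misranking is possible under the stated method. Call control A, CHW with CMAM B, and CHW with the combined/simplified protocol C.

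**Inputs.** Cure rates of 75% for A and 85% for C are the control and intervention recovery rates in section 3.2.1. The 84% for B, every unit cost and every transfer rate are assumptions, chosen only to show the mechanism.

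**Formula.** ICER of j over i = (C_j − C_i) / (E_j − E_i), with C the cost per child and E the cure proportion.

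**1. Comparator.** Assumed costs per child: A 100, B 110, C 125.

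- B vs A: (110 − 100) / (0.84 − 0.75) = 10 / 0.09 = 111 per extra cure
- C vs A: (125 − 100) / (0.85 − 0.75) = 25 / 0.10 = 250 per extra cure
- C vs B: (125 − 110) / (0.85 − 0.84) = 15 / 0.01 = 1,500 per extra cure

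At a willingness to pay between 250 and 1,500, both ratios against control look acceptable. Only the third shows that C is poor value over B.

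**2. Cost scope.** Assumed outpatient costs: A 140, B 150, C 145. Assumed transfer rates: A 7%, B 4%, C 7%. Let t be the cost of one transfer. Then

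- B vs A = (150 − 140 + (0.04 − 0.07)t) / 0.09 = (10 − 0.03t) / 0.09
- C vs A = (145 − 140 + 0 × t) / 0.10 = 50 for every t
- cost of C minus cost of B = −5 + 0.03t, with C curing 1 point more

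| t | B vs A | C vs A | C minus B (cost) | C vs B |
|---|---|---|---|---|
| 0 (transfers not costed) | 111 | 50 | −5 | C dominates B |
| 100 | 78 | 50 | −2 | C dominates B |
| 200 | 44 | 50 | +1 | 100 per extra cure |
| 300 | 11 | 50 | +4 | 400 per extra cure |
| 400 | B cheaper and better than A | 50 | +7 | 700 per extra cure |

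B becomes cheaper than C when t exceeds 5 / 0.03 = 167, and cheaper than control when t exceeds 10 / 0.03 = 333. The first row also bears on the comparator: B is dominated by C, yet still shows a finite 111 against control.

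**3. When the omission does not matter.** Transfers enter a cost difference as (difference in transfer rate) × t. If the rates are equal, the term is zero. That is why C vs A, both at 7%, stays at 50 throughout.

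**The case against.** **The scope sentence may only mirror eligibility.** Section 3.2.2 keeps children with complications at admission out of the sample, and leaving their costs out is consistent with that. Section 3.4 never mentions transfers. A reader might infer that the protocol deliberately drops the cost of later transfers, but the text does not establish that. What stands is that the sentence, taken literally, covers both groups and should say which it means.

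**Perspective concerns whose costs count, not which conditions are costed.** This is fair, so the fit with a societal perspective is poor rather than flatly contradictory.

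**The direction may be conservative.** If CHW care reduces complications, as section 5.1 expects, omitting transfers understates the savings of the CHW models against control. Section 5.1 does not separate the two CHW protocols, so nothing in the protocol predicts different transfer rates between them. The reversal shown above comes from assumed rates.

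**The contrast between CHW models is available by arithmetic.** Costs are to be shown per arm and recovery is compared between protocols. A reader might infer that the plan cannot show the CHW-combined versus CHW-CMAM increment, but that goes too far. The increment can be computed from the planned outputs. It is simply not announced, while the contrast with control is. The reference to doing nothing in section 3.4 rules out a null comparator and does not forbid further contrasts. An analysis plan could add detail, but the protocol itself fixes the ICER contrast, and fixes it too narrowly for a three-model objective.

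**Which children are costed.** A reader might also infer that children admitted on weight-for-height alone are costed in the CMAM arms while effects are limited to MUAC<115 mm. Section 3.4 does not say which enrolled children enter the costs, so this would be inference from silence, and it is not part of the point.

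**Conclusion.** The comparator part holds on the text. The stated ICERs are against control, the objective concerns three models, and no increment between the CHW models is announced. Ratios against control alone can make a dominated or poor-value model look acceptable.

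The cost-scope part is real but softer. It depends on reading the sentence literally, and it affects only children transferred after enrolment.

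No size can be derived from the protocol. The 250 versus 1,500 and the break-even of 167 per transfer are illustrations on assumed inputs. A reader might try to size the omission by assuming a 5-point difference in transfers and an inpatient episode costing 3 to 5 outpatient courses, giving 0.05 × 3 = 0.15 to 0.05 × 5 = 0.25 of an outpatient cost per child. Neither input has a source in the protocol, and the effect is nil if transfer rates are equal. The 7% inpatient share for Senegal in section 1.2 concerns all new SAM admissions, not transfers of enrolled children, so it cannot supply the rate.

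The point concerns a stated secondary aim meant to inform scale-up. It does not touch the non-inferiority comparison of recovery.

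**What to change.** 1. In section 3.4, order the three models by cost, remove dominated and extendedly dominated ones, and report each ICER against the next less costly model. Commit to reporting CHW-combined against CHW-CMAM. This uses costs and cures already planned per arm and is essentially free.
2. Reword the scope sentence so that children with complications at admission are outside the costing, in line with eligibility, and inpatient care after enrolment is inside it. Cost it as recorded transfers × a unit cost from the accounts. Transfers are already recorded as an outcome and accounting records are already a planned source, so this needs one further unit cost.
3. Add household costs of inpatient stays if an interview item can be included. The protocol describes no such collection, so this is a small extra burden.
4. If transfers cannot be costed, state the exclusion as a limit on the societal perspective and test it in the planned sensitivity analysis over a range of unit costs and transfer differences.
5. Reconcile the arm labels at the same time. Section 3.2.2 calls the combined/simplified arm intervention arm 2, while section 3.4 numbers the two intervention arms 2 and 3.

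### The cost-effectiveness analysis claims a societal perspective but, read naturally, leaves out the cost of enrolled children transferred to inpatient care, which biases the incremental cost if transfer rates differ between arms

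*Protocol*

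**What the plan says.** Protocol section 3.4 says of the cost-effectiveness analysis that "it will be carried out from a societal perspective". It then gives two limits on what is counted. The first is usual: "Costs linked to research only will be excluded". The second is the point here: "Cost will reflect only treatment of non-complicated SAM cases". The analysis will "calculate cost-efficiency and incremental cost-effectiveness ratio for children cured", comparing intervention arms with control, and will also use DALYs. A sensitivity analysis is announced without content.

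Four other places bear on this:

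- Section 3.2.2 (enrolment): the exclusion rule is the same for every arm and also covers severe edema. It reads in part: "failing appetite test or having other severe medical complications will be excluded (they will be referred for inpatient treatment". Every enrolled child therefore starts as uncomplicated.
- Section 3.2.3 (dependent variables): the rates compared between arms include "transfer to inpatient treatment due to health complications and death".
- Section 4.3 (emergencies), on complications during the study in any arm: "The program will bear medical expenses related to these interventions".
- Section 5.1 (expected results): the approach is expected to bring earlier diagnosis and care, "which could lead to a reduction in the development of medical complications and impact on the health costs for households".

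No section says that costs after transfer are charged to the arm from which the child came.

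**The concern.** A societal perspective counts resources whoever pays for them. An inpatient stay after a complication is such a resource, and so are the journey to hospital and the caregiver's time. If costing ends where the complication begins, they disappear from the arm in which the child was enrolled.

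This is more than a narrow cost list, because the cut-off is an event after randomisation. The arms differ in provider and protocol, and either could change how many children are transferred. If community health worker care reduces complications, as section 5.1 hopes, the rule hides the saving. If it leads to more transfers, the rule hides the extra cost. In both cases the numerator of the incremental ratio is wrong, in an analysis meant to inform scale-up.

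**Working it through.** **Step 1. What the sentence does.** Section 3.2.2 already keeps children who are complicated at presentation out of the sample. As a mere description of the sample, the sentence in section 3.4 would add little. It stands directly after the exclusion of research costs and it limits treatment cost, so it reads most naturally as a second exclusion. Nothing elsewhere restores the cost after transfer.

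**Step 2. Inputs for an illustration.** The protocol states no cost figure, no inpatient unit cost and no transfer rate, so there is nothing to reproduce. All of the following are assumptions:

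- full outpatient course = 1 unit
- share of the course used before transfer, f = 0.3
- inpatient episode = k units, k = 1 to 5
- transfer rate t = 3% in one arm and 7% in the other

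**Step 3. Mean cost per enrolled child.**

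Without inpatient care, (1 − t) + t·f:

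- t = 3%: 0.97 + 0.03 × 0.3 = 0.979
- t = 7%: 0.93 + 0.07 × 0.3 = 0.951

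The arm with more transfers looks 0.028 units cheaper (0.028 / 0.979, about 2.9%).

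With inpatient care, add t·k:

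| k | 3% arm | 7% arm | difference (7% minus 3%) |
|---|---|---|---|
| 1 | 1.009 | 1.021 | +0.012 |
| 2 | 1.039 | 1.091 | +0.052 |
| 3 | 1.069 | 1.161 | +0.092 |
| 5 | 1.129 | 1.301 | +0.172 |

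The order reverses whenever k > 1 − f = 0.7, that is, when an inpatient episode costs more than the outpatient care it replaces. The incremental cost left out is the difference in transfer rates times k: at k = 2, 0.04 × 2 = 0.08, which is 0.052 − (−0.028).

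**Step 4. Cost per child cured**, at k = 2.

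- Cure 85% in both arms. Excluded: 0.979 / 0.85 = 1.152 vs 0.951 / 0.85 = 1.119. Included: 1.039 / 0.85 = 1.222 vs 1.091 / 0.85 = 1.284. The order reverses.
- Each transfer removes one cure (82% vs 78%). Excluded: 0.979 / 0.82 = 1.194 vs 0.951 / 0.78 = 1.219. Included: 1.039 / 0.82 = 1.267 vs 1.091 / 0.78 = 1.399. The arm with more transfers already looks dearer, but the gap is understated.

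**Step 5. How small it could be.** Section 1.1 reports cured and defaulted children in the sponsor's earlier study in southern Mali: 94.2% + 4.5% = 98.7% with community health workers and 88.2% + 10.8% = 99.0% under standard care. If transfers were in those denominators (not stated), at most 1.3% and 1.0% remain for transfer, death and non-response together. The transfer rates could then differ by at most 1.3 points, and the omitted incremental cost at k = 2 would be at most 0.013 × 2 = 0.026 units per child. That study was outside a crisis area, so this is indicative only.

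**The case against.** The strongest reply is that non-complicated SAM is simply this trial's name for its population. The costing draws on accounting records, which may also contain children who were complicated at first contact, and the sentence may only be meant to remove them. It does not expressly say that costing of an enrolled child stops at transfer. This is a possible reading, and it is why the point should be put as a conflict to resolve. It does not remove the point: nothing in the protocol settles the matter, and an analyst following the text would leave the cost out.

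A second reply is that cost inventories are often left to a later analysis plan. That is fair for the details, but here the protocol itself fixes both the perspective and the limit, and the two do not fit together.

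Three stronger readings are tempting and are not supported:

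- A reader might take the 7% in section 1.2 as a transfer rate. It is the inpatient share of new routine SAM admissions in Senegal, not the rate at which outpatients are later transferred.
- A reader might conclude that the rule removes the item through which the models are expected to differ. Other drivers stay in scope: weight-based versus fixed RUTF quantities (section 3.2.2), shared iCCM costs, and household costs and treatment duration (section 5.1).
- A reader might infer from section 4.3 that households bear nothing after a complication. That section covers medical expenses only; it does not mention caregiver travel or lost time.

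**Conclusion.** The point holds in a limited form. The stated perspective and the stated cost limit conflict on the natural reading, and following the limit biases the incremental cost whenever transfer rates differ between arms. Cost per child is understated more in the arm with more transfers. It would go too far to say that this arm always looks cheaper: for cost per child cured, lost cures can offset or outweigh the apparent saving, although the gap between arms remains wrong.

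The size is unknown. In the illustration (3% vs 7%, f = 0.3, k = 2) the difference per child moves from −0.028 to +0.052 units; with transfer rates closer together it could be trivial. That inpatient care costs more than the outpatient care it replaces is also an assumption.

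Severity is moderate. Cost-effectiveness is the fourth specific objective, and the non-inferiority comparison of recovery is untouched.

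**What to change.** Replace the limiting sentence in section 3.4 with a rule along these lines:

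- The base case covers every child enrolled with uncomplicated SAM. Inpatient, transport and household costs after transfer are charged to the arm of origin, including medical expenses paid by the programme.
- These costs are valued as recorded transfers times a unit cost per country, varied in the sensitivity analysis already planned. This needs no individual follow-up beyond transfer, which section 3.2.3 does not describe.
- Only children who were complicated at first contact are left out.
- The outpatient-only scope is reported as a sensitivity analysis.

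If the sponsor prefers to keep the present limit, the perspective should be restated as narrower than societal, with a note that costs after transfer are not counted.

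The cost is small: a few unit costs per country (inpatient episode, transport, household), since transfers are already recorded. Mean cost per child will be higher in any arm with transfers, and not necessarily by little: in the illustration at k = 2 it rises from 0.979 to 1.039 and from 0.951 to 1.091. Sample size, treatment and visits do not change.

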The study aims to provide the first evidence on iCCM+Nut in emergency contexts by comparing the effectiveness and cost-effectiveness of two different decentralized models of care for uncomplicated SAM children. As indicated by previous studies, this could lead to a significant improvement in coverage and cost saving in the proposed crisis region where access to health services is a major issue. Results would contribute to strengthening the health systems in the country, and potentially the entire subregion in dealing with SAM care during protracted nutritional crisis as well as acute ones. This project also responds directly to various research gaps identified in ELRHA's systematic review on health interventions in humanitarian crises: "most effective way of delivering nutritional programmes: health facilities vs. CHWs", "Cost-effectiveness of nutrition interventions", "Effectiveness of different models of delivering (vertical vs. integrated)" and "Coverage and early detection related to SAM treatment".

In addition, the proposed research is also based on Action against Hunger (AAH) previous experience. In 2014, in partnership with the Ministry of Health (MoH), the *Institute National de Recherche et Santé Publique (INRSP)* of Mali, and the Innocent Foundation, AAH launched a study to explore whether CHWs could successfully treat SAM in the southern region (non-crisis area). The evidence showed that CHWs are able to reach high quality of care achieving better outcomes than CMAM (cured: 94.2% vs. 88.2%; defaulted: 4.5% vs. 10.8%), increasing the coverage by two-fold (baseline: 43.9%, endline: 86.7%) and demonstrating this is a cost-effective intervention with lower costs incurred by beneficiaries. Further similar studies are ongoing in Mauritania, Niger and Kenya. A second phase of Mali's study started in 2017 to determine the most efficient method of scaling up treatment with CHWs by comparing three different models of training and supervision.

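### The incremental cost-effectiveness ratio is defined only against control, so the two CHW models get no direct cost-effectiveness contrast although comparing them is a stated aim

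*Protocol*

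**What the plan says.** The rationale (section 1.1) gives the purpose of the study as "comparing the effectiveness and cost-effectiveness of two different decentralized models of care for uncomplicated SAM children". The fourth specific objective (section 2.2.2) is "To analyze cost and cost-effectiveness of three different models of SAM treatment".

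Section 3.4 is the only section that plans the cost-effectiveness analysis. It takes a societal perspective and promises: "We will present costs for different cost centres per arm". The incremental ratio is then defined by "comparing children in the intervention arms 2 and 3 vs. control arm with standard" care, and the sentence runs on: "CMAM protocol rather than a do nothing attitude) and DALYs". The section also states "A sensitivity analysis will be conducted", without saying what will be varied. It names no ratio between the two CHW arms, no ordering of the three options and no check for dominance.

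The contrast between the CHW arms does appear in section 3.2.3, as the second main independent variable: "Protocol applied in the case of CHWs areas (CMAM vs. Combined/Simplified". The dependent variables listed there are recovery, default, non-response, transfer and death. Cost is not among them.

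**The concern.** The three models are alternatives for the same health area, so a ministry can adopt only one of them there. For such a choice, the relevant ratio for each model is the one against the next less costly model that is not dominated. A ratio against a common baseline mixes a step that may be cheap (control to the first CHW model) with one that may be dear (the first CHW model to the second). A dearer CHW model can then look acceptable although its extra cost over the other CHW model buys few extra cures, or none.

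The uptake plan (section 5.2) wants the results to change national primary care policy. Which protocol the CHWs should use is part of that decision, and the ratios defined in section 3.4 do not answer it.

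**Working it through.** **No figure to reproduce.** The protocol states no cost per arm, no ratio and no threshold. What follows tests the rule under assumed costs.

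**Identity.** Let 0 be control, B the cheaper and C the dearer CHW model, with cost K and cures E per 100 children. With w = (E_B − E_0)/(E_C − E_0),

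ratio(C v 0) = w × ratio(B v 0) + (1 − w) × ratio(C v B).

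When C cures more than B and B more than control, the control-based ratio of C is therefore a weighted mean of the two steps. It is too low for the step from B to C whenever B has the lower ratio against control.

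**Inputs.**
- Control cures 88.2 and B cures 94.2 per 100, taken from the earlier Mali study in section 1.1.
- Assumed: B costs 600 more than control per 100 children, so its ratio is 600/6 = 100 per extra cure.
- Assumed: C costs 900 to 1,800 more than control and cures 94.7 to 98.2 per 100.

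| C cures | C extra cost v control | C v control | C v B | (C v B)/(C v control) |
|---|---|---|---|---|
| 94.7 | 900 | 138 | 600 | 4.33 |
| 94.7 | 1,200 | 185 | 1,200 | 6.50 |
| 94.7 | 1,800 | 277 | 2,400 | 8.67 |
| 95.2 | 900 | 129 | 300 | 2.33 |
| 95.2 | 1,200 | 171 | 600 | 3.50 |
| 95.2 | 1,800 | 257 | 1,200 | 4.67 |
| 96.2 | 900 | 112 | 150 | 1.33 |
| 96.2 | 1,200 | 150 | 300 | 2.00 |
| 96.2 | 1,800 | 225 | 600 | 2.67 |
| 98.2 | 900 | 90 | 75 | 0.83 |
| 98.2 | 1,200 | 120 | 150 | 1.25 |
| 98.2 | 1,800 | 180 | 300 | 1.67 |

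Check on the central row (95.2 cures, 1,200): w = 6/7, and 6/7 × 100 + 1/7 × 600 = 171. At an assumed threshold of 300 per extra cure, C passes against control (171) and fails against B (600).

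In the row with factor 0.83, B is extendedly dominated, because its ratio of 100 exceeds C's 90 and C cures more. Once B is removed, control is the right comparator for C and 90 stands. The sequential rule handles this case too.

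**Dominance.** Let C cure 93.2 at an extra 1,200. Against control this gives 1,200/5 = 240 per extra cure. Against B, C costs 600 more and cures 1 fewer, so it is dominated. The same pair of ratios, 100 and 240, also arises if C cures 95.2 at an extra 240 × 7 = 1,680. C is then not dominated, and its ratio against B is (1,680 − 600)/1 = 1,080. The two control-based ratios alone cannot tell these situations apart.

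**If both models save money.** Assume one saves 600 and cures 94.2, and the other saves 900 and cures 91.2. The ratios are −600/6 = −100 and −900/3 = −300. Negative ratios cannot be ranked, and the real trade-off is 300 saved for 3 fewer cures. A direct comparison is needed here as well.

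**Precision of the direct contrast.** Section 3.2.1 gives 576 children per arm, 96 per cluster and an intracluster correlation of 0.05. The design effect is 1 + 95 × 0.05 = 5.75. Near 85% cured, the standard error of the difference between two arms is √(2 × 0.85 × 0.15 × 5.75/576) = 0.050, or 5 percentage points. A ratio with a difference of about 1 point in its denominator would be unstable.

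**The case against.** Several points on the other side are sound.

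- **A reader might infer that the two CHW models are never compared.** The documents do not support that. Section 3.2.3 compares them on recovery and other outcomes, and section 3.4 presents costs per arm. A crude ratio could be derived by subtraction and division. What is missing is the planned contrast.
- **The control comparator is introduced to rule out a do-nothing baseline, and it excludes nothing else.** This is fair. An SAP could also set the ordering and the dominance checks. Even so, section 3.4 does state which arms enter the ratio, and that statement leaves out the comparison given as the aim in section 1.1.
- **The size rests on assumed costs.** This stands in full. The illustration also takes both CHW models to cost more than control, whereas section 1.1 cites RUTF spending of $36 against $68 per SAM child under integrated care. If a CHW model saved money, the harm would take the form of negative ratios that cannot be ranked.
- **A reader might infer that the arm labels conflict,** because section 3.2.2 writes "In the intervention arm 2, the combined/simplified protocol considers just bilateral pitting edema" while section 3.4 speaks of arms 2 and 3. The labels agree if control is arm 1. Figure 1, which would settle it, is not in the text at hand, so no contradiction is shown.
- **Cost-effectiveness is the fourth objective.** Allocation, sample size and data collection are untouched, and the remedy can be applied to data already planned.

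**Conclusion.** The point holds in a limited form. Section 3.4 defines the incremental ratio only against control and names no direct cost-effectiveness contrast between the two CHW models, although section 1.1 states that comparison as the aim and section 2.2.2 covers three models. Ratios against a common control can misstate the incremental ratio of the dearer CHW model and cannot by themselves show that one CHW model dominates the other.

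The algebra is general, but the size is not known. Under the assumed costs, the control-based ratio of the dearer model runs from about 8.7 times too low to slightly too high (factor 0.83). No single multiple should be read as an estimate of the bias in this trial. The distortion is large when the two models cure alike but cost differently. The protocol gives some reason to expect this: section 3.2.1 assumes one recovery rate of 85% for the intervention group, and section 3.2.2 gives the two CHW arms different RUTF regimens.

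It also does not follow that the wrong model will be chosen. The protocol has no threshold and no rule for choosing a model, so the documents support only that the planned ratios could mislead such a choice.

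**What to change.** In section 3.4, replace the control-only definition with a sequential one:

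1. Order the three arms by mean cost.
2. Remove dominated and extendedly dominated arms.
3. Compute each ratio, per child cured and per DALY, against the next less costly remaining arm.
4. Always report CHW-combined versus CHW-CMAM, whatever the ordering, as incremental cost, incremental effect and net benefit over a stated range of thresholds. Give uncertainty that allows for clustering. Net benefit is needed because a ratio with a near-zero effect difference is unstable.

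The ratios against control can stay as additional results. The cost is a few sentences and one more set of calculations on data already planned. Recruitment, sample size and data collection do not change.
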